Appendix 3. Investigators Global Assessment

The clinical evaluator of atopic dermatitis will perform an assessment of the overall severity of atopic dermatitis and assign an IGA score and category as described in the table below. The assessment will be a static evaluation without regard to the score at a previous visit.

IGA Score

Score	Category	Description*
0	Clear	Atopic dermatitis is cleared, except for any residual discoloration (post-inflammatory hyperpigmentation and/or hypopigmentation).
1	Almost Clear	Overall, the atopic dermatitis is not entirely cleared and remaining lesions are light pink (not including post inflammatory hyperpigmentation) and/or; have barely palpable hard thickened skin and/or papules and/or; have barely perceptible lichenification; excoriation and oozing/crusting are absent.
2	Mild	Overall, the atopic dermatitis consists of lesions that are light red; with slight, but definite hard thickened skin and/or papules; with slight, but definite linear or picked scratch marks or penetrating surface injury; with slight, but definite thickened skin, fine skin markings, and lichenoid scale; oozing/crusting is absent.
3	Moderate	Overall, the atopic dermatitis consists of lesions that are red; with easily palpable moderate hard thickened skin and/or papules; with moderate linear or picked scratch marks or penetrating surface injury; with moderate thickened skin, coarse skin markings, and coarse lichenoid scale; with slight oozing/crusting.
4	Severe	Overall, the atopic dermatitis consists of lesions that are deep, dark red; with severe hard thickened skin and/or papules; with severe linear or picked scratch marks or penetrating surface injury; with severe thickened skin with very coarse skin markings and lichenoid scale; with moderate to severe oozing/crusting.

* The IGA will exclude scalp, palms, and soles from the assessment/scoring.

Appendix 4. Eczema Area and Severity Index (EASI)

The EASI quantifies the severity of a subject's atopic dermatitis based on both severity of lesion clinical signs and the percent of BSA affected. EASI is a composite scoring by the atopic dermatitis clinical evaluator of the degree of erythema, induration/papulation, excoriation, and lichenification (each scored separately) for each of four body regions, with adjustment for the percent of BSA involved for each body region and for the proportion of the body region to the whole body.

Lesion Severity by Clinical Signs: The basic characteristics of atopic dermatitis lesions-erythema, induration/papulation, excoriation, and lichenification-provide a means for assessing the severity of lesions. Assessment of these four main clinical signs is performed separately for four body regions: head and neck, upper limbs, trunk (including axillae and groin) and lower limbs (including buttocks). Average erythema, induration/papulation, excoriation, and lichenification are scored for each body region according to a 4-point scale: 0=absent; 1=mild; 2=moderate; 3=severe. Morphologic descriptors for each clinical sign severity score are shown in the table below.

Clinical Sign Severity Scoring Criteria for the EASI

Score		Description*
Erythema (E)		
0	Absent	None; may have residual discoloration (post-inflammatory hyperpigmentation and/or hypopigmentation).
1	Mild	Light pink to light red
2	Moderate	Red
3	Severe	Deep, dark red
Induration/Papulation (I)		
0	Absent	None
1	Mild	Barely palpable to slight, but definite hard thickened skin and/or papules
2	Moderate	Easily palpable moderate hard thickened skin and/or papules
3	Severe	Severe hard thickened skin and/or papules
Excoriation (Ex)		
0	Absent	None
1	Mild	Slight, but definite linear or picked scratch marks or penetrating surface injury
2	Moderate	Moderate linear or picked scratch marks or penetrating surface injury
3	Severe	Severe linear or picked scratch marks or penetrating surface injury
Lichenification (L)		
0	Absent	None
1	Mild	Barely perceptible to slight, but definite thickened skin, fine skin markings, and lichenoid scale
2	Moderate	Moderate thickened skin, coarse skin markings, and coarse lichenoid scale
3	Severe	Severe thickened skin with very coarse skin markings and lichenoid scale

* The EASI will exclude scalp, palms, and soles from the assessment/scoring.

%BSA with Atopic Dermatitis: The number of handprints of skin afflicted with atopic dermatitis in a body region can be used to determine the extent (%) to which a body region is involved with atopic dermatitis (see table below). When measuring, the handprint unit refers to the size of each individual subject's hand with fingers in a closed position.

Handprint Determination of %BSA

Body Region	Total Number of Handprints in Body Region*	Surface Area of Body Region Equivalent of One Handprint*
Head and Neck	10	10%
Upper Limbs	20	5%
Trunk (including axillae and groin/genitals)	30	3.33%
Lower Limbs (including buttocks)	40	2.5%

Handprint refers to the hand size of each individual subject.

* The number of handprints will be for the entire body region; these values will not be adjusted for exclusion of scalp, palms, and soles from the BSA assessment.

EASI Area Score Criteria

Percent BSA with Atopic Dermatitis in a Body Region	Area Score
0%	0
>0 - <10%	1
10 - <30%	2
30 - <50%	3
50 - <70%	4
70 - <90%	5
90 - 100%	6

Body Region Weighting: Each body region is weighted according to its approximate percentage of the whole body (see table below).

EASI Body Region Weighting

Body Region	Body Region Weighting
Head and Neck	0.1
Upper Limbs	0.2
Trunk (including axillae and groin/genitals)	0.3
Lower Limbs (including buttocks)	0.4

* No adjustment for body regions excluded for assessment

In each body region, the sum of the Clinical Signs Severity Scores for erythema, induration/papulation, excoriation, and lichenification is multiplied by the Area Score and by the Body Region Weighting to provide a body region value, which is then summed across all four body regions resulting in an EASI score as described in Equation below.

$$\text{EASI} = 0.1A_h(E_h+I_h+Ex_h+L_h) + 0.2A_u(E_u+I_u+Ex_u+L_u) + 0.3A_t(E_t+I_t+Ex_t+L_t) + 0.4A_l(E_l+I_l+Ex_l+L_l)$$

A = Area Score; E = erythema; I = induration/papulation; Ex = excoriation; L = lichenification; h = head and neck; u = upper limbs; t = trunk; l = lower limbs

The EASI score can vary in increments of 0.1 and range from 0.0 to 72.0, with higher scores representing greater severity of atopic dermatitis.

Appendix 5. Scoring Atopic Dermatitis (SCORAD)

SCORAD is a validated scoring index for atopic dermatitis, which combines extent (0-100), severity (0-18), and subjective symptoms (0-20) based on pruritus and sleep loss, each scored (0-10).

Extent (A, maximum of 100%): To determine extent of AD, rule of 9 is used to calculate body surface area affected by AD as a percentage of the whole body surface area. Body surface area as percentage of total body surface area for each body region is as follows:

- Head and neck 9%;
- Upper limbs 9% each;
- Lower limbs 18% each;
- Anterior trunk 18%;
- Back 18%;
- 1% for genitals.

The score for each body region is added up to determine the BSA affected by AD (A), which has a possible maximum of 100%.

Severity (B, maximum of 18): A representative area of AD is selected. In this area, the severity of each of the following signs is assessed as none (0), mild (1), moderate (2) or severe (3).

- Erythema (reddening);
- Edema (swelling);
- Oozing/crusting;
- Excoriation (scratch marks);
- Skin thickening (lichenification);
- Xerosis (dryness) (this is assessed in an area where there is no inflammation).

The severity scores are added together to give 'B' (maximum of 18).

Subjective Symptoms (C, maximum of 20): Subjective symptoms, ie., itch and sleep loss, are each scored by the subject or caregiver using a visual analog scale (VAS) where “0” is no itch (or no sleep loss) and “10” is the worst imaginable itch (or sleep loss). The value for each should reflect the average on a 10-point scale for the last 3 days/nights. These scores are added to give 'C' (maximum score of 20).

SCORAD Total Score: The SCORAD for an individual is calculated by the formula: $A/5 + 7B/2 + C$ (can range from 0 to 103).

Appendix 6. A Weibull Proportional-Hazards Model for Event Time Data and Tipping Point Analysis

A Weibull Proportional-Hazards (WPH) Model

Let T_i be the time to event (observed or unobserved) and C_i the censoring time for subject i ($i = 1, 2, \dots, N$). We model the hazard function as,

$$h(t|x_i, \beta) = h_0(t)e^{\beta^T x_i}, \quad t > 0 \quad (1)$$

Here, β is a vector of unknown parameters corresponding to the vector of fixed effects x_i . There are three treatment groups, so the model term $\beta^T x_i$ when written out looks like,

$$\beta_1 x_{i1} + \beta_2 x_{i2}$$

Here, $x_{i1} = 1, x_{i2} = 0$ if subject i is randomized to PF-04965842 100 mg QD, $x_{i1} = 0, x_{i2} = 1$ if subject i is randomized to PF-04965842 200 mg QD and $x_{i1} = 0, x_{i2} = 0$ if subject i is randomized to placebo.

For further convenience, we also assume that $h_0(t)$ corresponds to the hazard function from the Weibull distribution with shape parameter $k > 0$ and scale parameter $\theta > 0$. So the survivor function $S(t; \beta^T x_i)$ amounts to,

$$\log(-\log S(t; \beta^T x_i)) = \beta^T x_i + k \log t - k \log \theta$$

In other words, this can be fit as a parametric regression model as,

$$\begin{aligned} \log t_i &= \log \theta - \frac{1}{k} \beta^T x_i + \frac{1}{k} \log(-\log S(t_i; \beta^T x_i)) \\ &= \beta_0 + \left(-\frac{\beta_1}{k}\right) x_{i1} + \left(-\frac{\beta_2}{k}\right) x_{i2} + \varepsilon_i \end{aligned}$$

with an intercept term as $\beta_0 = \log \theta$. Maximum likelihood estimates (MLE) for $\beta = (\beta_0, \beta_1, \beta_2)$ and k can be obtained using standard statistical software.

Tipping Point Analysis

Under censoring at random (CAR), $h(t|x_i, \beta)$ will be the same for all values of $t > 0$. If censoring is not at random (CNAR), then the post-censoring hazard $h^*(t|x_i, \beta), t > C_i$, will be different from $h^*(t|x_i, \beta), t \leq C_i$. We propose,

$$\begin{aligned} h^*(t|x_i, \beta) &= h_0(t) \exp\{\beta_1 x_{i1} + \beta_2 x_{i2}\}, \quad t \leq C_i \\ &= h_0(t) \exp\{\beta_1 (1 - \delta_1) x_{i1} + \beta_2 (1 - \delta_2) x_{i2}\}, \quad t > C_i \end{aligned}$$

When $\delta_1 = \delta_2 = 0$, we are in the CAR situation. For any other values of (δ_1, δ_2) , we have CNAR. In particular, when $\delta_1 = \delta_2 = 1$, we have a jump to reference situation where we assume that post-censoring, the hazard rate is no different from that in the placebo (reference) arm. We note also that this formulation assumes CAR for the placebo arm.

The corresponding survivor function $S^*(t; \beta^T x_i)$ is,

$$\begin{aligned} \log(-\log S^*(t; \beta^T x_i)) &= \beta_1 x_{i1} + \beta_2 x_{i2} + k \log t - k \log \theta, & t \leq C_i \\ &= \beta_1(1 - \delta_1)x_{i1} + \beta_2(1 - \delta_2)x_{i2} + k \log t - k \log \theta, & t > C_i \end{aligned}$$

The WPH model, as described in equation (1) above, will be used as the imputation model. Estimation of the model parameters will be performed under the Bayesian framework using Markov Chain Monte Carlo (MCMC) methods. We assign a non-informative prior for each component of $\beta = (\beta_0, \beta_1, \beta_2)$ to be independent and identically distributed as $\sim N(0, 10^6)$ and assign a weakly informative prior for the Weibull shape parameter $k > 0$ as an Inverse-Gamma distribution with shape= 10^4 and scale= 10^4 .

Let $\{\beta^b = (\beta_0^b, \beta_1^b, \beta_2^b), k^b: b = 1, 2, \dots, B\}$ be a sample (seed = 1848654157) from the posterior distribution. A single imputation \widetilde{T}_i^b of the unobserved (or censored) T_i is based on the posterior predictive distribution of the event times estimated from the WPH model. For example, if subject i is censored at C_i , \widetilde{T}_i^b must be sampled from the conditional distribution of $\widetilde{T}_i^b | \widetilde{T}_i^b > C_i$. This can be easily done by equating the conditional survivor function $S^*(t | t > C_i, \beta^{bT} x_i)$ to a uniform random variable and solving for t . Under our Weibull model, we draw $u_i \sim U[0, 1]$ and solve,

$$S^*(t_i | t_i > C_i, \beta^{bT} x_i) = \frac{S^*(t_i; \beta^{bT} x_i)}{S^*(C_i; \beta^{bT} x_i)} = u_i,$$

which has a simple closed form solution as,

$$\begin{aligned} k^b (\log t_i - \beta_0^b) \\ = \exp(\beta_1^b \delta_1 x_{i1} + \beta_2^b \delta_2 x_{i2}) \log \left\{ -\exp(-\beta_1^b x_{i1} - \beta_2^b x_{i2}) \log u_i + \left(\frac{C_i}{e^{\beta_0^b}}\right)^{k^b} \right\} \end{aligned}$$

Analysis of an imputed data set will produce an estimate as well as standard error of the hazard ratios using a Cox model as described in [Section 5.2.4](#). For given values of CNAR parameters (δ_1, δ_2) , this is repeated for B (typically, $B=500$) times to generate B complete imputed data sets and these B sets of estimates are combined using the Rubin's Method (Rubin, 1987). This can then be repeated for different values of MNAR parameters (δ_1, δ_2) to evaluate the impact of missing data. Note that $(\delta_1, \delta_2) = (0, 0)$ corresponds to an MAR analysis and $(\delta_1, \delta_2) = (1, 1)$ corresponds to an analysis commonly known as Jump-To-Reference (JTR).

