5.2.4. Analyses for Time to Event Data

For all time to event analyses, an origin and an accrual period will be defined (see table below), depending on the analysis populations. For a subject who experiences the event, the time to event will be the study day (relative to the origin being used for the analysis) corresponding to the actual date of the event or the earliest visit date at which the subject has already experienced the event. For all subjects who have not experienced the event and reached the end of the accrual period, their time to event will be right censored at the end of the accrual period. For subjects who permanently discontinue before the end of the accrual period without experiencing the event, their time to event will be considered missing data (see [Section 5.3.3](#) for handling of missing data in analysis).

	Origin	End of the Accrual Period
FAS-OL	Study Baseline	Last dose of open-label, run-in treatment
FAS-RA	First dose of randomized treatment	Last dose of randomized treatment
FAS-RE	Rescue Baseline	Last dose of rescue treatment

Time-to-event endpoints will be summarized using the Kaplan-Meier method and estimated survival curves will be displayed graphically. Graphs will describe the number of patients at risk over time. The median, quartiles and probabilities of not having an event at particular points in time will be estimated by the Kaplan-Meier method and their 95% CIs will also be provided when the data allows for their calculation. For some analyses, treatment differences between the probabilities of not having the event may be reported. Wald-type CIs for such differences will be reported using standard errors for the probabilities based on Greenwood's formula.

The log-rank test (stratified using age group [adults and adolescents] and disease severity [moderate and severe] at Study Baseline) p-value will be used for comparing time to event data between treatment groups.

For some analyses, a Cox regression model will be fit with treatment, age group and disease severity at Study Baseline as covariates. The estimated hazard ratio for the three pairwise treatment comparisons and its 95% CI will be reported from this model. For subgroup analyses, we will only have fixed effect of treatment in the model.

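### The tipping-point imputation model contains treatment only, while the Cox model fitted to the imputed data also adjusts for age group and severity, so the (0,0) starting point can differ slightly from the primary hazard ratio

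*SAP*

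**What the plan says.** SAP Section 5.3.3 censors early discontinuers at their last dose for the primary analysis and treats that censoring as at random. The tipping-point analysis of Appendix 6 is the planned sensitivity analysis of that assumption.

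In Appendix 6 the linear predictor is introduced with "There are three treatment groups, so the model term" and then written as two indicators, one for 100 mg and one for 200 mg, with placebo as reference. This model becomes the imputation model: "The WPH model, as described in equation (1) above, will be used as the imputation model". Priors are given for the intercept, the two treatment coefficients and the Weibull shape k ("We assign a non-informative prior for each component of" β; "assign a weakly informative prior for the Weibull shape parameter"). No coefficient for age or severity exists.

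The analysis step is different: "Analysis of an imputed data set will produce an estimate as well as standard error of the hazard ratios using a Cox model", namely the one in Section 5.2.4, where "a Cox regression model will be fit with treatment, age group and disease severity at Study Baseline as covariates". The primary test uses the same two factors: "The log-rank test (stratified using age group [adults and adolescents] and disease severity [moderate and severe] at Study Baseline) p-value will be used" for the comparison between arms.

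Appendix 6 labels the (0, 0) run as the censoring-at-random case and as an MAR analysis. Nothing else in the SAP adds age group or severity to the imputation model.

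**The concern.** An imputation model should contain the covariates of the model fitted to the imputed data. Here it does not, so all discontinuers in an arm have the same post-censoring hazard whatever their age or severity. The imputed times then carry no association with two factors that the SAP thinks worth adjusting for. At (0, 0) the method assumes that dropout is uninformative given treatment alone. The primary Cox model and stratified log-rank test need this only within levels of age group and severity.

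Two things can then move the treatment hazard ratio:

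- If dropout differs by severity between arms, the imputed data misstate the risk of those who left.
- Even without that, a treatment-only hazard ratio sits closer to 1 than an adjusted one when omitted factors are prognostic, and the imputed times inherit it.

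The two can pull in opposite directions. At stake is the interpretation of the scan. A tipping point is read as a distance from the primary result, and a displaced start mixes a model mismatch into that distance.

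**Working it through.** The plan gives no figure for the (0, 0) run, so there is none to reproduce. The check has four steps.

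**1. The printed draw at (0, 0).** With survivor function S(t) = exp{-exp(β'x)(t/θ)^k}, setting S(t)/S(C) = u gives

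(t/θ)^k = (C/θ)^k - exp(-β'x) log u.

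The closed form in Appendix 6 reduces to this when both deltas are 0. Any gap at (0, 0) therefore comes from what is in x and from k, not from the formula.

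**2. Large-sample size of the gap.** From the documents: 1:1:1 allocation, a 40-week blinded period, the two models above. Assumed, because the documents are silent: placebo median 12 weeks, exponential flare times, true hazard ratios 0.5 (100 mg) and 0.25 (200 mg), 40% severe, 18% adolescent, and the prognostic effects and dropout shown. k was estimated freely. Entries are the adjusted Cox hazard ratios, 100 mg / 200 mg.

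| Severity HR, adolescent HR, dropout | Censored data | Treatment-only imputation | With age and severity |
|---|---|---|---|
| 2, 0.7; 15% at 40 weeks, dropout hazard ×3 in severe active subjects | 0.499 / 0.253 | 0.492 / 0.251 | 0.500 / 0.253 |
| 2, 0.7; 30%, ×3 as above | 0.498 / 0.253 | 0.482 / 0.247 | 0.498 / 0.254 |
| 3, 0.5; 30%, ×3 as above | 0.500 / 0.252 | 0.482 / 0.246 | 0.501 / 0.252 |

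Imputed times were cut at 40 weeks in these rows. The SAP does not say whether they should be, so runs without the cut were also made; the shifts were similar or smaller.

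Without the concentration of dropout in severe active subjects, and with severity HR 3, adolescent HR 0.5 and about 22% of subjects imputed, 0.496 / 0.248 became 0.504-0.512 / 0.256-0.261. The severity hazard ratio fell from 2.99 to 2.11-2.46. With the covariates included, the result was 0.497 / 0.248.

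Extremes: 0.482/0.500 = 0.964, about -4%; 0.261/0.248 = 1.052, about +5%.

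**3. Trial size.** With 600 subjects, 100 imputations pooled by Rubin's rules and 40 simulated trials per setting:

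- Neither factor prognostic: mean log hazard ratio difference from the censored-data fit about 0.001.
- Prognostic factors, treatment-only imputation: root-mean-square difference 0.010-0.036, largest 0.08.
- Prognostic factors, covariates included: root-mean-square difference 0.003-0.007.

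**4. The prior on k.** For Inverse-Gamma with shape and scale 10^4, the mean is 10^4/(10^4 - 1) = 1.0001 and the SD is 1.0001/√(10^4 - 2) = 0.010. This prior fixes k at about 1. Steps 2 and 3 used exponential data (true k = 1), where this does no harm. A second design assumed two arms, hazard ratio 0.667, placebo median 20 weeks, severity HR 2, age HR 1.5, 40-week dropout of 40% in severe active subjects and 10% elsewhere, 40,000 subjects × 6 replicates, imputed times cut at 40 weeks and k held at 1:

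| True shape | Primary Cox | Treatment-only | With age and severity |
|---|---|---|---|
| 1.0 | 0.673 | 0.659 | 0.672 |
| 0.6 | 0.673 | 0.671 | 0.684 |
| 1.6 | 0.672 | 0.651 | 0.661 |

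When the true shape is not 1, adding the covariates under the printed prior leaves a gap, and at shape 0.6 it widens it. With k estimated freely the fit recovers. In the 12-week-median design with true shape 0.7, severity HR 2, adolescent HR 0.7 and 30% dropout, the censored data gave 0.497 / 0.249, and imputation with covariates gave 0.494-0.496 / 0.248-0.249.

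**The case against.** The strongest reply is that the SAP does not claim what a reader might infer. It calls (0, 0) a censoring-at-random analysis and never says that this run equals the primary analysis. Censoring at random given treatment is still censoring at random. This stands: the SAP's label is not false, but it names a different assumption from the one behind the primary Cox model. Exact reproduction of the primary test is also impossible, since that is a stratified log-rank p-value and Appendix 6 yields a Cox hazard ratio. Only the hazard ratio can be matched.

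A reader might also infer that the mismatch flatters the drug, so that the scan tips too late. The documents do not support a direction, because they give no dropout pattern. The shift favours the drug when severe active subjects leave more often, and goes the other way in the settings without that concentration.

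It is fair, too, that the effect is small. In the second design, with k estimated, severity HR 1.5, age HR 1.3 and dropout of 25% against 10%, the values were 0.666 for the primary Cox model and 0.661 after treatment-only imputation. With non-differential dropout of 20% or 30% the difference was below 0.003. The analysis is supportive and feeds no confirmatory test.

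Finally, the two covariates alone do not guarantee agreement with the primary hazard ratio while k is held near 1. Step 4 bears this out, so the prior has to change as well. None of this removes the mismatch between the two models, which is explicit in the text.

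**Conclusion.** The point holds as a minor inconsistency. The imputation model omits two covariates of the analysis model, so the start of the tipping-point scan can differ slightly from the primary Cox hazard ratio. The size, roughly -4% to +5% in either direction, rests on assumed severity hazard ratios up to 3, adolescent hazard ratios down to 0.5 and 40-week dropout settings of 15-30%, in some runs with the dropout hazard tripled in severe active subjects. None of these figures is in the documents. If neither age group nor severity predicts flare, the gap is nil.

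It would be wrong to infer that the primary result is in doubt: its estimate, p-value and the gatekeeping sequence do not use the imputation model. The gain from a change is a coherent reference point for the planned sensitivity analysis of missing flare times.

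**What to change.** In Appendix 6:

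- Extend the linear predictor to treatment plus age group (<18, ≥18) and Study Baseline severity (IGA 3, IGA 4), with the same N(0, 10^6) priors on the new coefficients.
- Keep δ1 and δ2 on the treatment terms only, and carry the two new terms through the survivor function and the closed-form draw.
- Replace the Inverse-Gamma(10^4, 10^4) prior on k with a genuinely weak one, so that the shape is estimated from the data.
- State that the (0, 0) hazard ratios will be compared with the primary Cox hazard ratios before the scan is read, and say whether imputed times are censored at the end of the 40-week period.

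The cost is two model terms, one prior and a few lines of SAP text. Both variables are already used in the primary analysis, so no new data are needed.

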After completing the 12-week rescue period, eligible subjects may enter study B7451015. Subjects discontinuing early from treatment, or who are otherwise ineligible for the LTE study will undergo a 4 week follow-up period in B7451014.

The total study duration if a subject does not flare is 52 weeks (12 weeks open-label treatment + 40 weeks blinded treatment). The maximum study duration is up to 64 weeks. This would only be achieved if a subject flared on the last day of the maintenance treatment period (52 weeks +12 weeks rescue). If subjects do not intend to enroll in the LTE study, the above durations are extended by +4 weeks of an untreated follow-up period.

A full schedule of activities for the study is provided in [Appendix 7](#).

Sample Size Determination

A total of 600 subjects with 200 receiving PF-04965842 200 mg QD, 200 receiving PF-04965842 100 mg QD, and 200 receiving placebo (1:1:1 randomization) will provide 94% power to detect a ratio of median time to flare of at least 1.5 times between either dose of PF-04965842 (200 mg or 100 mg) and placebo. The Type I error rate is set at 5% (2-sided). Assuming that about 44% of subjects would meet the protocol-defined criteria to be a responder at Week 12, (based on prior data), approximately 1370 subjects would need to enter the open label run-in period of the study to ensure that 600 subjects are available for randomization.

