5.3.3. Time to Event Endpoints

Subjects who reach the end of their accrual period without experiencing the event of interest will have their event times right censored at the end of their accrual period (ie, administrative censoring). Subjects who permanently discontinue before the end of their accrual period without experiencing the event of interest will have their event times considered missing.

For the primary analysis, these missing event times will be considered as right censored (censored at random) on their last date of dosing. As sensitivity analyses, tipping point analyses will be performed where these missing event times will be multiply imputed under an assumption of censoring not at random as proposed in Atkinson et al. (2019)¹ (see [Appendix 6](#)).

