6.1.1.2. Additional/Supportive Analyses

Additional analysis of the loss of response would be as:

- The time to loss of response will be analyzed using the methods in [Section 5.2.4](#) for the PPAS population.
- Missing time to loss of response will be multiply imputed under censoring not at random under a tipping point analysis framework using the methods in [Section 5.2.4](#) and [Appendix 6](#) for the FAS-RA population.

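### SAP Appendix 6 calls the prior on the Weibull shape weakly informative, but as printed it pins the shape at about 1

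*SAP*

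**What the plan says.** Appendix 6 assumes a baseline hazard that "corresponds to the hazard function from the Weibull distribution with shape parameter" k > 0 and scale θ, and notes that k and the regression coefficients have maximum likelihood estimates. For the Bayesian fit it will "assign a weakly informative prior for the Weibull shape parameter" k "as an Inverse-Gamma distribution with shape" 10^4 and scale 10^4. The regression coefficients get N(0, 10^6) priors.

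Dropouts' flare times are drawn from this model and analysed by Cox regression. This gives B (typically 500) "complete imputed data sets and these B sets of estimates are combined using" Rubin's method, and the process is repeated over a range of (δ1, δ2). At δ = 1, the jump-to-reference case, the post-censoring assumption is that "the hazard rate is no different from that in the placebo (reference) arm".

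The model serves one analysis. Under SAP 6.1.1.2, missing times to loss of response "will be multiply imputed under censoring not at random under a tipping point analysis framework". In the primary analysis (SAP 5.3.3), by contrast, "these missing event times will be considered as right censored". SAP Appendix 1 lists a single row under censoring not at random: loss of response in FAS-RA.

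**The concern.** A weakly informative prior should let the data determine k. Equal shape and scale of 10^4 do the opposite. Dropouts would then be imputed with a near-constant flare hazard whatever the observed curve showed, while a reader of the SAP would believe that the hazard shape had been estimated.

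This is the only planned analysis of the primary endpoint that relaxes censoring at random, so its stated properties should be true. If flares cluster early or late after randomization, the imputed flare probabilities of dropouts would be wrong, and the δ at which the result tips could move.

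**Working it through.** **Inputs from the documents.** Inverse-Gamma shape a = 10^4 and scale b = 10^4 (SAP Appendix 6). Three arms of 200, powered for a "ratio of median time to flare of at least 1.5 times between either dose" and placebo (SAP 2.2). The SAP states no summary of this prior, so there is no figure to reproduce.

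**1. Moments of the printed prior.**
- Mean = b/(a − 1) = 10,000/9,999 = 1.0001.
- SD = b/[(a − 1)√(a − 2)] = 10,000/(9,999 × √9,998) = 0.0100.
- 95% range 0.981 to 1.020; P(0.95 < k < 1.05) = 0.999999.
- Relative to k = 1, the log-density is lower by 268 at k = 0.8 and by 157 at k = 1.2.
- If scale instead meant the gamma scale of 1/k, k would sit near 10^-8 with SD 10^-10, so the label fails on that reading too.

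**2. Equivalent number of events.** For uncensored Weibull data Var(k̂) = 6k²/(π²n). At k = 1 and SD 0.010, n = 6/(π² × 0.0001) ≈ 6,080, about ten times the 600 planned subjects.

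**3. Can the data move k?** In single simulated trials of 3 × 200 over 40 weeks (assumed medians 20/30/30 weeks, 15% dropout):

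| True k | Events | Flat prior | 10^4 as printed | 10^-4 |
|---|---|---|---|---|
| 0.6 | 324 | 0.606 | 0.976 | 0.605 |
| 0.8 | 357 | 0.779 | 0.988 | 0.777 |
| 1.3 | 381 | 1.262 | 1.010 | 1.259 |
| 1.6 | 404 | 1.539 | 1.018 | 1.536 |

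**4. Effect on the sensitivity analysis.** Assumed, not in the documents: true k of 0.5, 0.7, 1, 1.5 or 2; placebo median 8, 16 or 30 weeks; 15% or 30% dropout over 40 weeks. The planned median ratio fixes HR = 1.5^(−k): 0.816, 0.753, 0.667, 0.544, 0.444. That gives 5 × 3 × 2 = 30 cells, each with 60 trials × 2 dose comparisons = 120, so 3,600 comparisons, with 100 imputations per trial. The analysis was a treatment-only Cox model with Rubin pooling; significant means z < −1.96. The printed prior was compared with Gamma(1,1), and a second imputation seed under Gamma(1,1) gave the noise level. Imputation used Appendix 6's post-censoring hazard. Its printed closed form agrees with that hazard at δ = 0 and was not used at other δ.

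With imputed times cut at Week 52:
- Posterior k (cell means): 0.95 to 1.04 under the printed prior, 0.50 to 2.03 under Gamma(1,1).
- Dropouts imputed to flare by Week 52 (δ = 0, placebo median 16 weeks, 15% dropout):

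| True k | Printed prior | Gamma(1,1) |
|---|---|---|
| 0.5 | 0.45 | 0.30 |
| 1 | 0.52 | 0.52 |
| 1.5 | 0.58 | 0.70 |
| 2 | 0.63 | 0.81 |

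- Shift in pooled HR over δ = 0 to 3: −0.016 to +0.018 for k from 0.5 to 1.5 (within 0.001 at k = 1), and −0.029 to +0.035 at k = 2. The largest was 0.470 against 0.436, at δ = 0, median 16, 30% dropout.
- Significance verdicts that differ: 41 of 3,600 at δ = 1 (seed noise 25) and 69 of 3,600 at δ = 3 (noise 32).

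**5. Where the tipping point moves.**
- Smaller effect than planned: HR 0.667 at k = 2, a median ratio of 0.667^(−1/2) = 1.22. At δ = 3, 482 against 515 of 720 remain significant; 47 differ (noise 6).
- No cut at Week 52 (Appendix 6 states none), planned ratio, six cells at 30% dropout: 6 of 720 verdicts differ at δ = 1 (noise 5), but 64 of 720 at δ = 3 (noise 1). Most of these are at k = 2 with median 30, where 18 against 64 of 120 are significant and the HR shift reaches +0.058.

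**The case against.** **The exponent may be a reading or typing slip.** A lost minus sign would resolve the conflict, and the documents cannot rule it out. Other minus signs in Appendix 6 survived, so loss is possible but not shown. This stands as a reason to check the source first.

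**The prior still has support k > 0, and Appendix 6 never promises an unconstrained k.** That is correct. The conflict is one of substance: the label and the estimable k imply that the data speak, and under the printed numbers they cannot.

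**The impact is slight, and the clear shifts need strong assumptions.** This largely stands. Against placebo, the post-censoring hazard is HR^(1−δ). At δ = 3 that is 0.667^(−2) = 2.25 times the placebo hazard in the smaller-effect setting and 0.444^(−2) = 5.06 times in the uncut k = 2 setting. A result that tips only there is already well past jump-to-reference. No document gives k, a placebo median or a dropout rate, and the results at non-zero δ follow the stated hazard, not the printed closed form. These points limit the size of the problem but do not make the label true.

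**Conclusion.** The point holds as a minor one. As printed, the prior is highly informative, with SD 0.010 around 1, and makes the Weibull imputation model exponential in practice. That part needs only the printed parameters and the planned sample size.

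The primary, key secondary and per-protocol results are untouched. If the flare hazard is close to constant, nothing changes. If it is not, dropouts' imputed flare probabilities shift materially, but the pooled hazard ratio moves little and the jump-to-reference conclusion is nearly unchanged at the planned effect. The tipping δ moves clearly only for an effect below the planned one, or beyond δ = 1 when imputed times run past Week 52. These sizes rest on the simulation assumptions listed above. Confidence is medium because the printed exponent itself needs confirming.

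**What to change.** Check the exponent in the source SAP and in the imputation program.

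- If 10^-4 was meant, correct the text and confirm that the program matches.
- If 10^4 stands, either replace it with a genuinely weak prior such as Gamma(1,1), or drop the label and state that the imputation assumes a near-constant hazard.

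Inverse-Gamma(10^-4, 10^-4) and Gamma(1,1) gave posterior k within 0.011 of each other in every simulated trial, so either serves. In all cases report the posterior mean and 95% interval of k beside the tipping-point table.

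The cost is one exponent, prior or label in the SAP and the program, plus one line of output.
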